Visit 4: All procedures as in visit 2 will be performed again, including dietary recall, targeted physical exam, and sample collection. All subjects will also get another oral FMT/placebo dose of 5 capsules each depending on their original assignment. All subjects in the study will get this intervention unless (a) they refuse the intervention (b) have undergone a liver transplant or have died/discharged to hospice (c) developed an infection or an SAE that was adjudicated to be related to FMT in the interim or (d) are currently undergoing antibiotic therapy for an infection that is not related to FMT.

For those who are infected due to an FMT-unrelated infection, we will approach the patients 2 days after the completion of the assigned antibiotic course. For those initiated on SBP (Spontaneous Bacterial Peritonitis) prophylaxis, we will provide the intervention after the initial SBP episode is treated. This may require delaying the intervention from day 30 to up to day 45 but this will still be counted as the second FMT.

All other subjects will be given the intervention and the blind will still be maintained. The brain function tests and QOL will be performed again. Groups 1 and 2 will get active FMT and groups 3 and 4 will get placebo FMT. No enemas will be given. The subjects will then be sent home.

Follow-up visits every month: The subjects will be followed monthly in person, or by phone or videoconference at Months 3, 4, 5 to evaluate dietary and medication changes and for safety analysis (hospitalizations, AEs or SAEs), targeted physical exam and for collection of samples at each study clinic visit. Mail-in kits for collection of stool, and urine will be provided along with instructions for use if visit is performed remotely. We will also perform the cognitive tests and QOL assessment at one month post-second intervention and at 6 months. We will continue to follow every patient for 6 months regardless of whether they developed an SAE or hospitalization in between. Only reasons not to follow them up for 6 months would be death, liver transplantation or patient withdrawal of consent.

End-of-Study visit: Per FDA mandates for FMT studies, we will see the patients at six months and we will evaluate AEs, interim hospitalizations, dietary recall, and perform targeted physical exam, QOL and brain function studies, and collect serum, and stool again. At this point the participation of the patient will end.

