3. The following will be recorded in all interventions (dose, Unit ID/Lot# of each treatment, Expiration Date and storage condition)

Number of interventions: One administration of rectal placebo or FMT and two administrations of oral FMT or placebo

We will ensure that each subject receiving active FMT will receive material (oral/rectal) from the same donor.

Duration of Follow-up after FMT: 6 months

Samples collected at baseline (before FMT), and at the visits specified above will be:

- a. Stool (microbiome, bile acid profile, metagenomics, metabolomics)
- Blood (CBC, Basic metabolic panel, LFTs, INR, endotoxin, and storage for circulating microbiome, systemic inflammatory markers, bile acids and metabolomics)
- c. Urine for metabolomics

Sample processing will be done using standard precautions at the McGuire VA Medical Center and samples will be stored for analysis of the secondary endpoints. Microbiota analysis will be performed at George Mason University and University of Minnesota, and metabolomics will be performed at the UC Davis NIH West Coast Metabolomics Center or Metabolon. We will perform the bile acid analysis at the McGuire VA Medical Center laboratories. Additional analyses at the Institute of Hepatology, London, UK, and the University of North Carolina at Chapel Hill. We may also use other referral laboratories as needed.

Statistical analysis: These will be performed using ANOVA of delta changes after intervention/follow-up using Chi-square and Fisher exact for non-parametric (hospitalizations, HE episodes, covert hepatic encephalopathy etc.), for continuous variables, and specialized bio-informatics analyses for the microbiota (see details below). These will be adjusted for age, gender, MELD score and alcoholic etiology of cirrhosis.

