Brain function: These will be administered at visit 1, visit 4 (one month after the second FMT), and end-of-study by [name] and the coordinator/research assistant. Two validated testing strategies, Psychometric Hepatic Encephalopathy Score (PHES) and EncephalApp Stroop Test, which have norms for the Virginia population will be used¹⁸. The PI and his team are well-published in this field and have been administering these for several years to cirrhotic patients. Both these tests showed benefit in the FMT enema trial published by our group in HE¹⁰. PHES is a recommended battery that defines brain dysfunction in cirrhosis¹⁹. It consists of 5 paper and pencil tests (number connection tests A and B, digit symbol test, line tracing test and serial dotting tests), which form a composite score of standard deviations below an age/education-matched community healthy population. This gives a score ranging between -15 and +4. In addition to this continuous score, covert hepatic encephalopathy can be diagnosed with a score <-4 for our population¹⁸. This test battery takes 15 minutes to complete. EncephalApp Stroop^{18, 20} is a freely available computerized test which consists of an easier "Off" state and a more difficult "On" state. The OffTime+OnTime is the output, which is the time taken to complete 5 correct runs in the Off and On states. The output here can be continuous (seconds in the

OffTime+OnTime) or covert hepatic encephalopathy percentage based on local norms¹⁸. This takes 5-7 minutes to complete.

Quality of Life: This will also be administered at Visit 1, Visit 4, one month after the second FMT, and End-of-Study visit. The Sickness Impact Profile (SIP)²¹ is a validated profile for QOL in cirrhosis that the PI and his team have had several years of published experience²²⁻²⁴. SIP consists of 136 questions that pertain to any issues that patients have experienced in the last 24 hours. It has a composite score, two dimensions (physical and psycho-social) and twelve individual domains that are calculated based on norms. A higher score indicates a worse quality of life. This gives only a continuous score as the output. A copy is shown in the Appendix. [name] and the coordinator/research assistant will perform these.

Endpoints and Plan of Analysis:

Primary Endpoint: FMT-related SAEs including HE recurrence within 6 months

Secondary Endpoints (details below):

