- 1. Safety-related (at 6 months): Liver-related hospitalizations, other serious adverse events (SAE) and adverse events related to interventions.
- 2. Microbiota composition: Stool 16SrRNA sequencing and engraftment of donor into recipients.
- Inflammatory milieu: Endotoxemia (LAL), Systemic inflammatory cytokines (IL-6, TNF, IL-1b using ELISA)
- 4. Bile acid profile and gut-liver mediators expression: Bile acid profile using LC/MS in stool and serum and serum C4 (7α-Hydroxy-4-cholesten-3-one).
- 5. Urinary metabolomics to evaluate gut-microbial markers
- 6. Brain function: Two validated testing strategies, PHES and EncephalApp Stroop Test, and Quality of Life: Sickness Impact Profile (a validated profile for healthrelated quality of life in cirrhosis)

Adjudication: Data and safety monitoring for this study will be provided by the Clinical Science Research & Development (CSR&D) centralized Data Monitoring Committee (DMC). The DMC is provided by CSR&D to ensure independent oversight of the safety and integrity of the project. The DMC is an independent multidisciplinary group, whose members have collectively – through research, education, training, experience, and expertise – the requisite knowledge pertinent to the subject areas to be reviewed. Membership details are available on the CSRD website. The DMC will provide an ongoing independent evaluation of this study focused on safety and feasibility, including participant accrual and retention, adverse events monitoring, and data analyses. Meetings will be held three times per year at which recommendations will range from approval to continue (unconditionally or with conditions to be addressed) to probation or possibly termination, if there are problems with enrollment or safety concerns

All outcomes will be compared between groups as well as post-intervention to baseline.

Visits at VCU and VAMC:

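### Continuous secondary outcomes with several follow-ups get only an ANOVA of change, with no named visit, no baseline covariate and no use of a patient's other scores

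*Combined protocol and SAP*

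**What the plan says.** The Statistical analysis paragraph sets the method for continuous outcomes: "These will be performed using ANOVA of delta changes after intervention/follow-up". Apart from bioinformatics for the microbiota, nothing else is offered. On covariates it says "These will be adjusted for age, gender, MELD score and alcoholic etiology of cirrhosis". Endpoints and Plan of Analysis adds only "All outcomes will be compared between groups as well as post-intervention to baseline".

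These outcomes are longitudinal:

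- **SIP** (Specialized analyses, Quality of Life): "This will also be administered at Visit 1, Visit 4, one month after the second FMT, and End-of-Study visit". That is three times after baseline.
- **Cognition.** The Brain function paragraph lists two times after baseline, because it treats Visit 4 as the assessment one month after the second FMT. Under Procedures, the second dose is given at Visit 4, where testing is also repeated. The monthly follow-up paragraph then says "We will also perform the cognitive tests and QOL assessment at one month post-second intervention and at 6 months", which makes three.
- **Samples:** "Samples collected at baseline (before FMT), and at the visits specified above will be" stool, blood and urine. This covers day 15, day 30, later visits and the end of study, although the End-of-Study paragraph does not list urine.

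On missing data, the monthly follow-up paragraph says "Only reasons not to follow them up for 6 months would be death, liver transplantation or patient withdrawal of consent". For remote visits it says "Mail-in kits for collection of stool, and urine will be provided along with instructions for use if visit is performed remotely". The documents contain no repeated-measures model, no rule for missing values, no principal time point for these outcomes and no multiplicity rule.

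**The concern.** An ANOVA of change takes one change per patient. With two or three follow-ups, the plan therefore yields two or three answers per outcome and does not say which one counts. The team's earlier enema trial shows why this matters. Its MELD table tests change separately at days 6, 12 and 35, with p-values of 0.004, 0.3 and 0.04, so the conclusion depends on the visit chosen.

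A change also needs both values. With no rule for missing values, a patient without the later value leaves that test, and the scores already collected in between go unused. Gaps are foreseeable:

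- Remote visits have no kit for blood.
- Patients withdrawn before day 30 are said to be followed for safety, with no mention of cognitive or quality-of-life scores.
- The individual halting rules include overt HE, non-elective hospitalization and a MELD rise of 8, so loss of data could follow deterioration.

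Brain function and quality of life are part of the overall objective and of secondary aim 3. With 25 patients per arm, little information can be spared.

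**Working it through.** **1. The plan's own figures.** It gives power only for hospitalization: 100, 98 and 94% at 25, 20 and 15 per group. A four-group chi-square test with rates of 80/30/30/10% at α = 0.05 gives 99.7, 98.8 and 94.9%, so those figures reproduce. They say nothing about the continuous outcomes, for which the documents give no effect size, correlation or drop-out rate. The inputs below are assumptions, apart from 25 per arm (Sample size paragraph): effect 0.8 SD, equal correlation ρ of 0.5 to 0.7 between all visits, 5 to 35% missing at month 6, two-sided α = 0.05.

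**2. What the baseline covariate is worth.** For a score with SD 1, the change from baseline has variance 2(1 − ρ). The baseline-adjusted score has variance 1 − ρ². The ratio is (1 + ρ)/2, which is 0.75 at ρ = 0.5 and 0.85 at ρ = 0.7. Power for one pair is about Φ(0.8/√(2v/n) − 1.96). For example, with v = 1 and n = 25: 0.8/√0.08 = 2.83, and Φ(0.87) = 80.7%. With values missing at random times and completers only:

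| n per arm | ρ = 0.5, change (v = 1.00) | ρ = 0.5, adjusted (v = 0.75) | ρ = 0.7, change (v = 0.60) | ρ = 0.7, adjusted (v = 0.51) |
|---|---|---|---|---|
| 25 (none missing) | 80.7% | 90.4% | 95.5% | 97.7% |
| 23.75 (5%) | 78.7% | 88.9% | 94.5% | 97.1% |
| 16.25 (35%) | 62.6% | 75.0% | 83.7% | 89.1% |

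Much of the available gain therefore comes from adding the baseline, before any other visit is used.

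**3. Drop-out that depends on earlier scores.** This was simulated with two arms of 25, a baseline and three follow-ups. Drop-out was monotone, half before the second follow-up and half before the third, with a log-odds slope of 1 per SD.

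- *Drop-out follows the previous score level* (ρ = 0.7; 15/25/35% missing). ANOVA of change estimates 0.798/0.798/0.805, so there is no bias. Its power is 92/88/82%. A repeated-measures model with baseline as covariate has 95/92/89%. The same model on raw scores without baseline has only 77/73/72%.
- *Drop-out follows worsening from baseline* (15 to 35% missing). ANOVA of change estimates 0.76 to 0.71 at ρ = 0.5, and between 0.78 and 0.72 at ρ = 0.7. At worst, (0.80 − 0.71)/0.80 = 11% too small; at 5% missing the shortfall is about 2%. The model with baseline stays at 0.79 to 0.81. At ρ = 0.5, power is 70 to 54% by ANOVA against 86 to 74% by the model in one run; a second run gave 72% for the model at 35% missing.
- *Few missing* (5%, ρ = 0.7): 94% against 97%.

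Over all these settings the ranges are about 54 to 94% for ANOVA of change and 72 to 97% for the model with baseline.

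**4. Several visits, each tested at 0.05.** If the tests were independent, the chance of at least one false positive would be 1 − 0.95² = 9.75% for two visits and 1 − 0.95³ = 14.3% for three. Changes share a baseline and are correlated. Simulated four-arm ANOVAs with ρ from 0.5 to 0.8 give 8.8 to 9.5% for two visits and 12.5 to 13.1% for three.

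**The case against.** The plan does not say that every visit will be tested or that patients will be dropped. Both are inferred from the method and from the absence of any other rule. The inference is fair, because a change needs two values and no visit is singled out, but it remains an inference.

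The assumed drop-out has no source in the documents. In the earlier enema trial, described as the same population, all 20 subjects completed five months, and this protocol follows patients to six months despite SAEs. If only 5% are missing, the loss is small.

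Naming one visit would cure the multiplicity under ANOVA just as well. A repeated-measures model does not cure it unless one contrast is named. Nor is any mixed model an improvement: on raw scores with only the planned covariates, power is about 70 to 78% at ρ = 0.7, against 83 to 92% for the planned ANOVA. Such a model also treats scores after death as if they were merely unobserved. These points stand, and they shape the fix.

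A reader might infer that the month-6 ANOVA is biased whenever sicker patients leave. Under drop-out on score level, a comparison of raw month-6 scores would indeed show 0.74 to 0.70 instead of 0.80. The plan analyses change, however, which is unbiased in that setting. A reader might also infer larger shrinkage, to 0.61 at 30% missing (ρ = 0.5). That needs drop-out in the comparator arm only, and nothing in the documents points to it.

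**Conclusion.** The point holds for the continuous secondary outcomes. The plan names no visit as the result, leaves out each outcome's own baseline, and has no way to use the other scores of a patient who misses a visit. On the stated assumptions, power for one pair is about 54 to 94% as planned, against 72 to 97% with a baseline-adjusted repeated-measures model, much of the difference being due to the baseline. Bias of about 2 to 11% toward no effect arises only if drop-out follows worsening from baseline. The chance of a false positive per outcome is about 9 to 10% with two tested visits and 12 to 13% with three.

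The documents give no drop-out rate, correlation or effect size, so these are ranges and not forecasts. The primary endpoint, FMT-related SAEs including HE recurrence, is untouched. The change is worth making because it is cheap and did better in every setting examined.

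**What to change.** For PHES, EncephalApp, SIP and the serum markers, replace ANOVA of change by one mixed model for repeated measures per outcome. Include group, visit, group-by-visit, the outcome's own baseline, baseline-by-visit and the covariates already planned, and use all observed visits. Specify a simpler covariance structure in case the unstructured one does not converge.

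Name one contrast per outcome as the result and report other visits as supportive. Month 6 would suit PHES, EncephalApp and SIP. For each biomarker, choose a visit at which that sample is actually collected. Reconcile the Brain function paragraph with Procedures on whether there are two or three assessments after baseline.

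State that scores after death or transplantation are not treated as ordinary missing values, and add a sensitivity analysis.

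The cost is plan wording and standard software, with no new visits or patients. The downside is the model's assumption that missing values are predictable from observed scores.

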Sponsor-Investigator:

[name], MS Associate Professor, Virginia Commonwealth University and McGuire VA Medical Center,

[name],

[name]

[contact]

[contact]

Email: [contact]

Study Title:

Fecal MicrobiotaTransplantation in Cirrhosis and Hepatic Encephalopathy

IND #18578

Date: October 14, 2020

Amendment 4

Protocol Number: [name]

Product: Fecal Microbiota Preparations vs Placebo From Molecular and Cellular Therapeutics (GMP) facility at the University of Minnesota.

Proposed Indication: Cirrhosis and Hepatic Encephalopathy

SCIENTIFIC BACKGROUND

Indication: Cirrhosis and hepatic encephalopathy

Study Objectives: To evaluate the safety and tolerability of fecal transplant in patients with cirrhosis and hepatic encephalopathy

Rationale and Supporting Evidence:

Hepatic encephalopathy affects 30-45% of patients with cirrhosis and adversely affects survival in these patients¹. The mainstay of treatment for hepatic encephalopathy (HE) has long been the manipulation of the gut flora through antibiotics, prebiotics or probiotics². The current first and second line therapies for HE in the US are lactulose and rifaximin respectively that uniquely act within the confines of the gut lumen with encouraging clinical results. However, there is a subset of patients with HE that continues to recur despite being on both treatments³. This patient group is at a higher risk of poor outcomes because HE has now been removed from liver transplant priority and multiple episodes of HE can result in cumulative brain injury which may be irreversible⁴. Therefore, the prevention of recurrent HE is an important therapeutic goal. Our group and other reports have shown that patients with HE and cirrhosis are more likely to have overgrowth of potentially pathogenic bacterial taxa such as Enterobacteriaceae and reduction of autochthonous species such as Lachnospiraceae and *Ruminococcaceae* in the stool and the colonic mucosa⁵⁻⁸. This has been linked to poor performance on cognitive tests that are a hallmark of HE and with increased systemic inflammation in these patients^{6, 7}.

Therefore, a gut-based therapeutic option that can potentially improve the recurrence rate and the overall prognosis is needed. Fecal transplant has been shown to be

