Ruminococcaceae. In our published experience, a single enema from a rationallyderived donor was associated with significantly lower total and HE-related hospitalizations compared to patients who were randomized to standard of care, with a stable long-term course over >1 year¹⁰. Our data show that FMT was associated with favorable changes in fecal bile acid (BA) profile with a decrease in proportions of fecal secondary BAs, conjugated BAs and increase in sulfated BAs, indicating a healthier milieu. We also have preliminary data defining the safety of oral FMT capsules in patients with cirrhosis and HE in a current trial led by us¹¹. The use of combined oral *and rectal routes of FMT, which can potentially alleviate both small bowel and colonic translocation are likely to be better than either alone*.

Details of the team's experience with FMT in cirrhosis using enema¹⁰:

In the trial conducted by us under IND 16452, we have recruited 20 subjects with cirrhosis and recurrent HE (the same population proposed for this trial). All subjects completed the 5-month follow-up without SAEs that were associated with FMT. The baseline subject characteristics are:

	No-FMT group	FMT group	P value
	(n=10)	(n=10)	
Age	62.9±9.8	64.5±5.1	0.65
Gender (Men/Women)	10/0	10/0	1.0
Race (Caucasian, African- American, Hispanic, others)	6/3/1/0	7/2/1/0	0.9
MELD score	13.2±3.7	12.0±2.9	0.36

None of the subjects reached a grade of 3 or change in >2 of any of their GI symptoms throughout the study. Similarly, none of the subjects developed clinically relevant hepatic encephalopathy or significant changes in liver chemistries or labs (WBC

>12,000 or <1000/ml, MELD >8 increase, AST/ALT/ALK>10 times ULN). As shown in the table below, there was a significant improvement (reduction in the MELD score) in the FMT group compared to the no-FMT group at day 1 post-FMT (day 6) and day 30 post-FMT (day 35) compared to baseline. No changes in the WBC count were observed.

	No-FMT group	FMT group	P value
	(n=10)	(n=10)	
MELD score			
Day 0 minus day 6	0.6±1.4	-1.5±1.4	0.004
Day 0 minus day 12	0.4±1.3	-0.2±1.3	0.3
Day 0 minus day 35	1.2±2.4	-0.9±1.7	0.04
Serum WBC count			
Day 0 minus day 6	-0.1±0.6	0.1±1.2	0.60
Day 0 minus day 12	-0.53±0.9	0.2±1.0	0.10
Day 0 minus day 35	0.22±0.5	0.2±0.9	0.95

There was a significant reduction in hospitalizations and improvement in brain function in patients randomized to FMT+ antibiotics compared to those randomized to SOC¹⁰.

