Aerobes	Fresh	2.53E+05	1.76E+05
	1 freeze-thaw	4.30E+05	4.43E+05
Anaerobes	Fresh	5.80E+07	3.96E+07
	1 freeze-thaw	6.20E+07	5.29E+06

CFUs per mL of Capsules G3 Microbial Emulsion Matrix

_CFUs per mL of stool homogenized 1:1 (w/v) with buffer containing 12.5% glycerol and 0.9% saline, after one freeze-thaw cycle

	per mL
Aerobes	4.53E+06
Anaerobes	1.47E+09
Spores	2.00E+06

These concentrations will be used for the upcoming trial to ensure that the material concentrations in our older trials are expanded.

- We anticipate providing 5 capsules at a time for the oral FMT and 60ml of the FMT enema.
- The placebo for the oral FMT will be made using identical capsules as the active drug, except it will contain 10%/weight trehalose (the cryoprotectant used in preparation of freeze-dried microbiota) and the rest carboxymethylcellulose. Since the capsules are not transparent and have no specific smell or taste, there should be no difficulty in maintaining double blinding.
- The placebo for the liquid formulation is non-bacteriostatic, sterile phosphate buffered saline containing 10% USP grade glycerol. Each dose will be packaged in individual cryobags, just as the active drug.

Study Design

Overall objective: To determine the effect of dual oral and rectal administration of FMT from a rational donor on clinical outcomes (hospitalizations, brain function, quality of life) and host-microbiota interactions (microbial composition and bile acid composition with systemic and intestinal inflammation), compared to single route of administration and placebo, along with a second oral capsular FMT vs placebo administration in patients with cirrhosis and HE using a randomized, phase II clinical trial.

Design overview:

Four groups of outpatients with cirrhosis will be randomized using random sequence generator into placebo and FMT groups and followed for 6 months under an FDA IND double-blind clinical trial.

Group 1: Dual oral and rectal FMT, Group 2: Oral FMT and rectal placebo, Group 3: Oral placebo and rectal FMT and Group 4: Oral and rectal placebo

A repeat oral capsular FMT vs placebo based on the group assignments above will be provided to every subject in at day 30.

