The primary aim is: To evaluate the safety and tolerability of fecal transplant through rectal and oral capsular routes in cirrhosis and HE from a liver disease and symptom standpoint using analysis of serious adverse events, especially HE recurrence, in a placebo-controlled trial.

Secondary aims are between the groups:

- 1. Safety and tolerability of FMT compared to placebo
 - a. Frequency, severity and relatedness of solicited and unsolicited AEs through day 30
 - b. Occurrence of new potentially transmitted infections through six-months post FMT
 - c. Occurrence of new onset or significant worsening of chronic medical conditions post-FMT
- 2. To define the changes in microbiota composition and function of the stool microbiota after FMT compared to pre-FMT baseline and donor compared to placebo

- 3. To evaluate changes in systemic inflammatory cytokines and endotoxin, quality of life and cognitive function compared to pre-FMT baseline and compared to placebo
- 4. To determine occurrence of new onset or significant worsening of chronic medical conditions through six months post-FMT and compared to placebo
- 5. To evaluate the changes in the microbiota after the second oral FMT vs. placebo compared to baseline values

Inclusion/Exclusion Criteria:

Inclusion criteria:

- A. Cirrhosis diagnosed by either of the following in a patient with chronic liver disease
 - a. Liver Biopsy
 - b. Radiologic evidence of varices, cirrhosis or portal hypertension
 - c. Laboratory evidence of platelet count <100,000 or AST/ALT ratio>1
 - d. Endoscopic evidence of varices or portal gastropathy
 - e. Fibroscan values suggestive of cirrhosis
- B. On treatment for hepatic encephalopathy (patient can be on lactulose and rifaximin)
- C. Age: at least 21 years of age
- D. Able to give written, informed consent (demonstrated by mini-mental status exam>25 at the time of consenting)
- E. Women of child bearing potential must agree to use effective contraception for the duration of the study and for 10 days prior and 30 days after the study
- F. Negative pregnancy test in women of childbearing age

Exclusion criteria:

- A. MELD score >22
- B. WBC count <1000 cells/mm3
- C. Platelet count < 25,000/mm3
- D. TIPS in place for less than a month
- E. Currently on antibiotics apart from rifaximin
- F. Infection at the time of the FMT (diagnosed by blood culture positivity, urinalysis, paracentesis as needed)

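### Baseline rifaximin use is optional at entry and relevant to HE, but it is neither a stratification factor nor a named covariate, so a chance imbalance between arms of 25 would go unadjusted

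*Combined protocol and SAP*

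**What the plan says.** - **Entry.** Inclusion criterion B reads "On treatment for hepatic encephalopathy (patient can be on lactulose and rifaximin"). It permits rifaximin and does not require it. Exclusion criterion E reads "Currently on antibiotics apart from rifaximin", and item 3 of the safety-related exclusions repeats the exemption. Users and non-users can both enroll.
- **Relevance.** Rationale and Supporting Evidence names lactulose and rifaximin as first- and second-line HE treatments that work inside the gut. It motivates the trial by saying that "there is a subset of patients with HE that continues to recur despite being on both treatments". The account of the earlier enema trial describes its subjects as having "cirrhosis and recurrent HE (the same population proposed for this trial"). No criterion requires recurrence on both drugs.
- **Randomisation.** Under Design overview the patients "will be randomized using random sequence generator into placebo and FMT groups". Procedures gives the ratio as 1:1:1:1. No stratification factor appears in either place.
- **Analysis.** Statistical analysis plans ANOVA of changes for continuous outcomes, and chi-square and Fisher exact tests for hospitalizations, HE episodes and covert HE. It then says: "These will be adjusted for age, gender, MELD score and alcoholic etiology of cirrhosis". Rifaximin appears in no model, stratum or subgroup.
- **Endpoints.** The primary endpoint is FMT-related SAEs including HE recurrence within 6 months. Hospitalization, cognition and microbiota, including donor engraftment, are compared between groups.

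**The concern.** Rifaximin use at entry is plausibly prognostic in two ways: it marks patients whose HE needed a second drug, and it is itself an active treatment at the site where FMT acts. It could bear on HE recurrence, hospitalization, cognition and engraftment.

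The protocol elsewhere treats antibiotic exposure as relevant to outcome. Sample size raises the assumed FMT hospitalization rate from 20% to 30% because the earlier trial gave antibiotics first. The section on microbial diversity reports a collapse after antibiotics that recovered with FMT. Those passages concern other antibiotic courses, not rifaximin, but they make it odd to leave the one permitted background antibiotic out of the analysis.

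With 25 subjects per arm and no stratification, the share of users can differ noticeably between arms by chance. If it does, a reader will ask how much of an arm difference in HE events is due to rifaximin, and the plan has no prespecified answer. A covariate chosen after the imbalance has been seen is less convincing than one named in advance.

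**Working it through.** **Inputs from the documents.** 25 per arm, four arms; alpha 0.05 (taken as two-sided, since the plan does not say); planned 6-month hospitalization rates of 80% (control), 30% (each single route) and 10% (dual route).

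**Inputs assumed.** The documents give neither the prevalence of rifaximin use nor its effect. Prevalence p is varied from 50% to 90%, and the risk difference between users and non-users from 10 to 30 points.

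**Step 1: the plan's own power.** The stated figures are 100%, 98% and 94% at 25, 20 and 15 per group. An overall four-group chi-square (3 df) at 80/30/30/10% has noncentrality n × Σ(pᵢ − 0.375)² / (0.375 × 0.625), which is 28.5 at n = 25. Power is 99.7%, 98.8% and 94.9%. An 80% vs 20% comparison by the arcsine method gives 99.5%, 98.3% and 94.1%. The stated figures are therefore reproduced to within about a point. For single pairs at 25 per arm (two-sided test, pooled variance under the null), power is 96.7% for 80% vs 30% and 42.1% for 30% vs 10%.

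**Step 2: chance imbalance.** Let X₁ and X₂ be independent Binomial(25, p) counts of users. A gap of 20 points is 5 subjects (5/25). The SD of the difference in proportions is √(2p(1 − p)/25). The last column is the exact probability that the largest and smallest of the four arms differ by at least 5 subjects.

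| p | SD of difference | P(gap ≥ 20 points), given pair | P(gap ≥ 20 points), any of six pairs |
|---|---|---|---|
| 50% | 14.1 points | 20% | 58% |
| 60% | 13.9 points | 19% | 56% |
| 70% | 13.0 points | 16% | 50% |
| 80% | 11.3 points | 11% | 38% |
| 90% | 8.5 points | 3% | 14% |

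**Step 3: effect on an arm difference.** Shift = imbalance × risk difference = 0.20 × 0.10 to 0.20 × 0.30 = 2 to 6 points, in either direction.
- Against 80% vs 30% (50 points) this is 2/50 to 6/50, or 4% to 12% of the contrast.
- Against 30% vs 10% (20 points) it is 2/20 to 6/20, or 10% to 30%.
- The standard errors are √((0.8 × 0.2 + 0.3 × 0.7)/25) = 12.2 points and √((0.3 × 0.7 + 0.1 × 0.9)/25) = 11.0 points. A 6-point shift is therefore about half a standard error.

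**Step 4: what adjustment buys.** Trials were simulated (40,000 per case; p of 50%, 70% and 80%; risk differences of 10, 20 and 30 points). The unadjusted chi-square was compared with a Mantel-Haenszel test stratified by rifaximin.

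| Setting | Unadjusted | Stratified |
|---|---|---|
| No effect (50% vs 50%), all trials: rejection | 6.3–6.6% | 4.7–5.1% |
| No effect, trials with imbalance ≥ 20 points: rejection | 6.8–9.3% | 4.4–5.4% |
| 80% vs 30%: power | 96.7–97.3% | 96.2–97.9% |

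The unadjusted level over all trials hardly moves with the size of the rifaximin effect. Its excess over 5% comes from using the uncorrected chi-square at this sample size. The rise that can be put down to rifaximin is seen only among trials with a large imbalance. Stratifying changes power by about 1 point or less.

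**The case against.** The strongest reply is that randomisation already handles this. Imbalance is random error counted in the test's level, it is as likely to work against FMT as for it, and the simulation shows no overall inflation from rifaximin. This stands. A reader might infer from the omission that the HE and microbiota comparisons are confounded; the documents do not support that. What remains is lost precision, and weaker validity given an imbalance that has actually occurred.

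Other parts of the reply:
- **Size.** Both prevalence and effect are assumed. The rationale and the reference to recurrent HE suggest that use could be high, and at 90% the problem is minor. The 38% to 58% figures describe the worst of six pairs, not a named comparison. This stands and limits the claim.
- **Protection elsewhere.** Change from baseline removes part of a stable rifaximin effect on continuous outcomes. The causality assessment may weigh concomitant drugs, and medication changes are reviewed at the monthly follow-up contacts. This stands in part: change scores do nothing for HE recurrence or hospitalization, nor for an effect on engraftment, and event-level attribution does not adjust a comparison of arms.
- **The covariate list.** A reader might take the four covariates as exhaustive. The sentence does not say so, although it names no others.
- **Gender.** The earlier enema trial enrolled only men, which might suggest giving gender's place to rifaximin. That does not follow: this protocol provides for women in inclusion criteria E and F and recruits non-Veterans through VCU.
- **Why rifaximin rather than another factor.** Prior HE episodes or TIPS might also be prognostic, and MELD is already listed. The choice is a judgment. It rests on the protocol's own description of rifaximin and its exemption from the antibiotic exclusions.

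**Conclusion.** The omission is real and its consequence is modest. Rifaximin use can vary at entry, the protocol itself treats it as an active gut-directed HE therapy, and neither the randomisation nor the named covariates account for it. With 50% to 80% use, a given pair of arms has an 11% to 20% chance of differing by 20 points or more, and the resulting shift is 2 to 6 points if the risk difference is 10 to 30 points. This does not threaten the 80% vs 30% comparison. It matters more for dual vs single route, where the planned difference is 20 points and pairwise power is about 42%.

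The finding implies neither biased results nor a wrong sample size. It is a cheap improvement that is best made before unblinding.

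**What to change.** In Statistical analysis, before unblinding:

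1. Add baseline rifaximin use (yes/no) to the existing covariates, keeping gender, for the continuous cognition and microbiota comparisons.
2. For HE recurrence and hospitalization, name a test stratified by rifaximin (for example Mantel-Haenszel) or a regression model. Extending the covariate list alone would change nothing here, because chi-square and Fisher exact tests adjust for no covariate. Event counts bear on the choice: at the planned rates, dual vs one single route has 25 × 0.10 + 25 × 0.30 = 10 expected hospitalized subjects, too few for a model with many covariates, so the stratified test is safer for that pair.
3. Report baseline rifaximin use by arm.
4. For any subjects not yet randomised, stratify the 1:1:1:1 sequence by rifaximin use, in blocks.

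The cost is one degree of freedom and slightly more analysis work. Rifaximin use must already be known to apply inclusion criterion B and the antibiotic exclusion, so no new data are collected, and the sample size is unchanged. Rifaximin started or stopped after randomisation is a separate question that these steps do not address.
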